#### 3.1 Introduction

Although localized sarcoma is potentially curable, approximately 50% of subjects with large or high-grade tumors will ultimately develop incurable disease. This is a pilot study to examine the addition of the anti-PD-1 targeted, monoclonal-antibody pembrolizumab to standard, neoadjuvant radiation for subjects with high-risk soft tissue sarcomas planning for surgery with curative intent. Pembrolizumab has been combined in the past using hypofractionated radiation, but has never been combined with conventionally fractioned radiation with curative intent in soft tissue sarcoma subjects before. This trial will confirm the safety of this novel combination. A large randomized trial would be required to definitively demonstrate a relapse-free-survival benefit in this population. This study will instead focus on characterizing T-cell responses to this neoadjuvant combination, with a particular focus on the repertoire of tumor infiltrating lymphocytes (TIL). Tumor necrosis and radiographic response by RECIST criteria will be used as surrogates for efficacy, as has been done in other pilot trials combining radiation with novel therapies.

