Flow cytometry or multiplex IHC may be performed on both pre and post treatment samples in order to quantify T cell infiltrates and characterize T cell phenotype. Expression of inhibitory markers (PD-1, CTLA-4, LAG-3) will be tested on infiltrating T cells. Additionally, stromal immune cells will be characterized with respect to tumor associated macrophage phenotype (CD163, CD115, CD206). Expanded lymphocytes will be tested to determine tumor specificity against a single cell suspension made from the resection specimen. PBMC from pre and post treatment samples will be tested to determine if changes in T cell phenotype observed in the tumor are observed systemically. Additional or alternative analysis of tumor or blood specimens may be completed at investigator discretion.

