## 10.0 STATISTICAL ANALYSIS PLAN

### 10.1 Statistical Analysis Plan Summary

The rationale for combining radiation and immunotherapy has been written about extensively . However, these studies have focused on hypofractionated radiation in the metastatic setting and none of these published studies have examined the use of Pembrolizumab with the neoadjuvant radiation schedules that are typically used in the curative setting for many malignancies. Safety will be evaluated by CTCAE 5.0 and tabulated for qualitative description.

With regards to efficacy analysis, RECIST evaluations will be performed and tabulated in both qualitative and quantitative formats. This is a pilot trial that is not powered to give definitive determination of efficacy. As RECIST partial responses are not typically seen following neoadjuvant radiation alone, any objective responses would be highly interesting and encouraging of further study either for soft-tissue sarcomas generally or for a specific subtype where a response was observed.

The rate of complete necrosis will also be analyzed. It is assumed that the rate of complete necrosis in this subject population is approximately 15% after chemoradiation . A design with 26 subjects has 94.4% power to detect an improvement in the complete necrosis rate from 15% to 40%. The observation of at least 7 subjects with complete necrosis would be considered evidence to rule out a 15% complete necrosis rate. With 26 subjects, binary proportions can be estimated to within 20%. Any toxicity with at least 10% prevalence has at least a 94% chance of being observed.

Event free survival and overall survival at 1 and 5 years will be determined in order to estimate the potential benefit in the highest risk subjects. We will generate Kaplan Meier curves to illustrate these overall survival rates and event-free survival rates. Using data already being analyzed under IRB approved protocols, we will compare these to historical controls at our institution using Cox's proportional hazard model. Subjects' demographic variables (such as age and gender) will be incorporated in the analysis.

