Biologic specimens will be compared using gene expression, flow cytometry and mIHC between pre and post treatment samples. This data will be utilized to quantify cellular infiltrates and create a detailed profile of T cell and macrophage phenotypes. For most samples, it is expected to obtain sufficient cell counts to flow sort live single cell suspension samples, CD45 neg (tumor) populations, and CD4+, CD8+ and CD11B+ populations for RNA extractions so that the RNAseq results on individual cellular populations may be compared.

The study center is experienced in expanding tumor infiltrating lymphocytes (TIL), and in most cases is able to expand TIL to numbers sufficient for functional assays. All tumor samples will be subject to TIL expansion. If tumors demonstrate defined immunogenic antigens, cytokine release assays will be performed to interrogate changes in T cell function

between pre and post treatment samples. If relevant, either expanded TIL or single cell suspension samples may be sent for TCR sequencing to determine how therapy impacts the TCR repertoire.

A historical series has been collected of such samples treated with radiation alone (protocol #9013) and the change in these two data sets will be compared using two-sample T-test. Pathway analysis tools (such as Gene Set Enrichment Analysis) may also be used to evaluate if relevant biological pathways (such as immun-response pathways) show any alterations with respect to the therapy. Kaplan Meier curves depicting genes of interest, mIHC results and clinical outcomes will be reported. Cluster analysis based on gene expressions may be performed, and followed by the conduct of subtype analysis, where appropriate. Gene expression's impact on the survival time will be evaluated, if appropriate, and its AUC (area under the curve) will be reported if such biomarkers show up in analysis.

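### Gene-expression AUCs against survival are reported only for markers that emerge from the analysis, on the same 26 or fewer subjects, with no multiplicity control or internal validation

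*Combined protocol and SAP*

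**What the plan says.** All of this is in the last part of Section 10.1 unless stated otherwise.

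- Survival analysis: "Gene expression's impact on the survival time will be evaluated, if appropriate", followed by the statement that "its AUC (area under the curve) will be reported if such biomarkers show up in analysis". The plan does not say what counts as showing up, how many candidates there are, or whether the AUC is binary, at a landmark time or time-dependent. It mentions no interval.
- Candidates: RNA is to be extracted from several sorted cell populations "so that the RNAseq results on individual cellular populations may be compared", alongside flow cytometry and multiplex IHC. Section 9.4.5 leaves the list open: "Additional or alternative analysis of tumor or blood specimens may be completed at investigator discretion".
- Comparison with the radiation-alone series (protocol #9013): "the change in these two data sets will be compared using two-sample T-test". No alpha or multiplicity rule is attached. Validation of a selected marker is not among the stated uses of that series.
- Subjects: the trial has 26, and sufficient cell counts are expected for most samples rather than all.

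Neither Section 10.1 nor any other section mentions false-discovery or family-wise control, permutation, cross-validation, a hold-out set or external validation of a biomarker.

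**The concern.** An AUC calculated on the subjects who were used to pick the marker is biased upward, because the picking favours markers that fit this sample's noise. Reporting only the markers that emerge hides how many were tried, so a reader cannot discount for the search. With few subjects and potentially thousands of expression values, the bias can be most of the reported effect. At stake is how far the biomarker findings can be trusted: an AUC that looks strong could be what noise alone produces, and nothing in the planned report would show the difference.

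**Working it through.** **The plan's own figure.** The plan gives no figure for a biomarker AUC. The figure tied to the 26 subjects is the primary-endpoint power: "A design with 26 subjects has 94.4% power to detect an improvement in the complete necrosis rate from 15% to 40" percent, with the rule "The observation of at least 7 subjects with complete necrosis would be considered evidence to rule out a 15% complete necrosis rate". Exact binomial: P(X ≥ 7 | n = 26, p = 0.40) = 0.944, which reproduces it; P(X ≥ 7 | n = 26, p = 0.15) = 0.083. This confirms n = 26 and has no other role here.

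**Inputs.**
- n = 26 (Section 10.1).
- Events e: not planned. Section 3.1 puts eventual incurable disease at about 50% for large or high-grade tumors, so about 0.50 × 26 = 13 in the long run and fewer at one year. Assumption: 7-10, with 4 and 13 as outer cases.
- Candidates m: not stated. Assumption: 50, 770 or 5,000, with 20 to 20,000 as the outer range.
- No gene has any true association, so the true AUC is 0.50.

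**Step 1: one noise gene.** AUC = [R − e(e+1)/2] / [e(n − e)], where R is the rank sum of the gene's expression among the e subjects with an event. Either direction counts, so the larger of AUC and 1 − AUC is taken. The exact null chance p of 0.9 or more is 0.0071 (4 events), 0.00100 (7), 0.00033 (10) and 0.00017 (13). For a single gene named in advance, an AUC of 0.9 would be surprising.

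**Step 2: the best of m noise genes.** With independent genes the chance that the best reaches 0.9 is 1 − (1 − p)^m. For m = 770 and 7 events, 1 − (1 − 0.00100)^770 = 0.54. Mean best AUCs are from simulation; the higher end is for 7 events.

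| Candidates | Mean best apparent AUC, 7-10 events | Chance best ≥ 0.9, 7 events | Chance best ≥ 0.9, 10 events |
|---|---|---|---|
| 50 | 0.78-0.81 | 0.05 | 0.02 |
| 770 | 0.88-0.90 | 0.54 | 0.22 |
| 5,000 | 0.92-0.94 | 0.99 | 0.81 |

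**Step 3: sensitivity** (median best value, no true signal).
- 20 genes: 0.83 (4 events) to 0.74 (13). 20,000 genes: 1.00 to 0.93.
- Correlated genes (blocks of 100, correlation 0.8), 1,000 genes: 0.93, 0.86 and 0.83 at 4, 7 and 13 events, against 0.97, 0.91 and 0.87 for independent genes.
- Harrell's C in place of a binary AUC, 1,000 genes: 0.95, 0.86, 0.82 and 0.78 at 4, 7, 10 and 13 events.
- All markers passing an unadjusted p < 0.05, rather than the best one: mean AUC 0.87, 0.80 and 0.77 at 4, 7 and 13 events.

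**Step 4: unadjusted tests.** If tests are run gene by gene at 0.05, the expected number of null genes declared is 0.05 × m: 2.5 of 50, about 38 of 770, 250 of 5,000.

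**Step 5: do the remedies work on null data?** With 7 or 10 events and 50 to 5,000 genes:
- Leave-pair-out resampling with the gene re-selected each time gives a mean AUC of about 0.46-0.56, as it should. Its SD between null data sets is about 0.21-0.27.
- The bootstrap optimism correction, even with selection repeated in each resample, still gives about 0.61-0.74. It does not remove the bias here.

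**The case against.** The strongest reply is that the plan does not describe a genome-wide screen. Section 10.1 speaks of genes of interest, optional pathway analysis and optional clustering, and the survival sentence is doubly conditional. A short candidate list fits the text equally well. This stands: a gene-by-gene screen is an inference, and so is a gene-level reading of the t-test. What can be said from the text is that the selection rule is undefined and nothing limits the list.

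A second reply is that the work is exploratory. That also stands as to consequence: Section 4.3 lists gene expression only as a change in immune infiltrates, the predictor endpoint in Section 5.3 concerns imaging, and no decision in the trial uses an AUC. It does not remove the bias. Exploratory status excuses low power, not a reporting rule that inflates the estimate. The pilot disclaimer in Section 10.1 concerns power for efficacy, not biomarker selection.

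A reader might infer from Section 3.1 ("This study will instead focus on characterizing T-cell responses to this neoadjuvant combination") that prognostic gene AUCs are a main aim. The text does not go that far: it concerns T-cell responses and the repertoire of infiltrating lymphocytes. Nor do the documents say that these AUCs will guide the next trial. Section 6.2.3.1 ties a randomized trial to the complete-necrosis rate, and Section 10.1 ties further study to objective responses.

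**Conclusion.** The concern holds as a defect of an exploratory analysis. Section 10.1 makes AUC reporting depend on the result, uses the same 26 or fewer subjects for selection and evaluation, and gives no multiplicity control or internal validation. If many genes are screened, noise alone gives a best apparent AUC of about 0.78-0.81 with 50 candidates, 0.88-0.90 with 770 and 0.92-0.94 with 5,000, against a true 0.50. This rests on assumed candidate counts, 7-10 events, a binary outcome and independent genes; a concordance index or correlated genes give somewhat lower values.

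A reader might conclude that pure noise will yield AUCs near 0.9. The documents do not support that as a general statement, because they size neither the panel nor the events. The figure describes the best marker from a large panel, not the typical reported marker and not a short list. The primary endpoint and its decision rule are unaffected.

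**What to change.** Amend Section 10.1, before the biomarker data are examined, as follows:

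1. Report gene-level tests, including any gene-level use of the t-test against the radiation-alone series, with Benjamini-Hochberg adjusted p-values and the number of genes tested.
2. State the type and time point of the AUC. Compute it by cross-validation (for example leave-pair-out or repeated k-fold) with the selection step repeated inside every fold, and show it with an interval beside the apparent AUC. Do not offer the bootstrap optimism correction as an alternative, since it leaves substantial bias in this setting.
3. Report the result for every gene screened, not only for those that emerge.

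No subject, visit or sample changes. The cost is a paragraph of wording and a little more code. The downside is fewer and less striking biomarkers, and wide intervals: even at the lower SD of 0.21, two SDs either side of 0.50 run from 0.08 to 0.92. A single cross-validated AUC from 26 subjects will therefore say little by itself, and the interval is needed to make that visible.

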## **11.0 LABELING, PACKAGING, STORAGE AND RETURN OF CLINICAL SUPPLIES**

### **11.1 Investigational Product**

The Sponsor-Investigator shall take responsibility for and shall take all steps to maintain appropriate records and ensure appropriate supply, storage, handling, distribution and usage of investigational product in accordance with the protocol and any applicable laws and regulations.

Clinical Supplies will be provided by Merck as summarized in Table 8.

Table 8 - Product Descriptions

Product Name & Potency	Dosage Form
Pembrolizumab 50 mg	Lyophilized Powder for Injection
Pembrolizumab 100 mg/ 4mL	Solution for Injection

### **11.2 Packaging and Labeling Information**

Clinical supplies will be affixed with a clinical label in accordance with regulatory requirements.

### **11.3 Clinical Supplies Disclosure**

This trial is open-label; therefore, the subject, the trial site personnel, the Sponsor and/or designee are not blinded to treatment. Drug identity (name, strength) is included in the label text; random code/disclosure envelopes or lists are not provided.

#### **11.4 Storage and Handling Requirements**

Clinical supplies must be stored in a secure, limited-access location under the storage conditions specified on the label.

Receipt and dispensing of trial medication must be recorded by an authorized person at the trial site.

Clinical supplies may not be used for any purpose other than that stated in the protocol.

#### **11.5 Returns and Reconciliation**

The Sponsor-Investigator is responsible for keeping accurate records of the clinical supplies received from Merck or designee, the amount dispensed to and returned by the subjects and the amount remaining at the conclusion of the trial.

Upon completion or termination of the study, all unused and/or partially used investigational product will be destroyed at the site per institutional policy. It is the Sponsor-Investigator's responsibility to arrange for disposal of all empty containers, provided that procedures for proper disposal have been established according to applicable federal, state, local and institutional guidelines and procedures, and provided that appropriate records of disposal are kept.

### **12.0 DATA AND SAFETY MONITORING PLAN**

Institutional support of trial monitoring will be in accordance with the FHCC/University of Washington Cancer Consortium Institutional Data and Safety Monitoring Plan. Under the provisions of this plan, FHCC Clinical Research Support (CRS) coordinates data and compliance monitoring conducted by consultants, contract research organizations, or FHCC employees unaffiliated with the conduct of the study. Independent monitoring visits occur at specified intervals determined by the assessed risk level of the study and the findings of previous visits per the institutional DSMP.

In addition, protocols are reviewed at least annually and as needed by the Consortium Data and Safety Monitoring Committee (DSMC), FHCC Scientific Review Committee (SRC) and the FHCC/University of Washington Cancer Consortium Institutional Review Board (IRB). The review committees evaluate accrual, adverse events, stopping rules, and adherence to the applicable data and safety monitoring plan for studies actively enrolling or treating subjects. The IRB reviews the study progress and safety information to assess continued acceptability of the risk-benefit ratio for human subjects. Approval of committees as applicable is necessary to continue the study.

The trial will comply with the standard guidelines set forth by these regulatory committees and other institutional, state and federal guidelines.

## **13.0 ADMINISTRATIVE AND REGULATORY DETAILS**

### **13.1 Institutional Review Board**

In accordance with federal regulations (21 CFR 312.66), an Institutional Review Board (IRB) that complies with regulations in 21 CFR 56 must review and approve this protocol and the informed consent form prior to initiation of the study.

### **13.2 Consent**

The Sponsor-Investigator or his associate must explain verbally and in writing the nature, duration, and purpose of the study and possible consequences of treatment. Subjects must also be informed that they may withdraw from the study at any time and for any reason without jeopardizing their future treatment. In accordance with federal regulations (21 CFR 312), all subjects must sign the IRB-approved consent form.

### **13.3 Termination of Study**

The Sponsor-Investigator reserve the right to terminate this study at any time. The FDA may also terminate the study.

### **13.4 Compliance with Trial Registration and Results Posting Requirements**

Under the terms of the Food and Drug Administration Modernization Act (FDAMA) and the Food and Drug Administration Amendments Act (FDAAA), the Sponsor of the trial is solely responsible for determining whether the trial and its results are subject to the requirements for submission to the Clinical Trials Data Bank, <http://www.clinicaltrials.gov>. Information posted will allow subjects to identify potentially appropriate trials for their disease conditions and pursue participation by calling a central contact number for further information on appropriate trial locations and trial site contact information.

## 15.0 APPENDICES

### 15.1 Appendix A: Performance Status

#### 15.1.1 ECOG Performance Status

Table 9 - ECOG Performance Status

Grade	Description
0	Normal activity. Fully active, able to carry on all pre-disease performance without restriction.
1	Symptoms, but ambulatory. Restricted in physically strenuous activity, but ambulatory and able to carry out work of a light or sedentary nature (e.g., light housework, office work).
2	In bed <50% of the time. Ambulatory and capable of all self-care, but unable to carry out any work activities. Up and about more than 50% of waking hours.
3	In bed >50% of the time. Capable of only limited self-care, confined to bed or chair more than 50% of waking hours.
4	100% bedridden. Completely disabled. Cannot carry on any self-care. Totally confined to bed or chair.
5	Dead.

\*As published in Am. J. Clin. Oncol.: *Oken, M.M., Creech, R.H., Tormey, D.C., Horton, J., Davis, T.E., McFadden, E.T., Carbone, P.P.: Toxicity And Response Criteria Of The Eastern Cooperative Oncology Group. Am J Clin Oncol 5:649-655, 1982.* The Eastern Cooperative Oncology Group, Robert Comis M.D., Group Chair.

### 15.1.2 Karnofsky Performance Status

Table 10 - Karnofsky Performance Status

Karnofsky Status	Karnofsky Grade
Normal, no complaints	100
Able to carry on normal activities. Minor signs or symptoms of disease	90
Normal activity with effort	80
Care for self. Unable to carry on normal activity or to do active work	70
Requires occasional assistance, but able to care for most of his needs	60
Requires considerable assistance and frequent medical care	50
Disabled. Requires special care and assistance	40
Severely disabled. Hospitalization indicated though death no imminent	30
Very sick. Hospitalization necessary. Active supportive treatment necessary	20
Moribund	10
Dead	0

From oncologypro.esmo.org: As published in Am J Clin. Oncol.: Oken, M.M., Creech, R.H., Tormey, D.C., Horton, J., Davis, T.E., McFadden, E.T., Carbone, P.P.: Toxicity And Response Criteria Of The Eastern Cooperative Oncology Group. Am J Clin Oncol 5:649-655, 1982. The Eastern Cooperative Oncology Group, Robert Comis M.D., Group Chair.

## 15.2 Appendix B: Women of Childbearing Potential Definitions and Methods of Contraception

### 15.2.1 Definitions

#### 15.2.1.1 Woman of Childbearing Potential (WOCBP)

A woman is considered fertile following menarche and until becoming postmenopausal unless permanently sterile. Permanent sterilization methods include hysterectomy, bilateral salpingectomy, and bilateral oophorectomy.

#### Women in the following categories are not considered WOCBP

- Premenarchal
- Premenopausal female with 1 of the following:
  - Documented hysterectomy
  - Documented bilateral salpingectomy
  - Documented bilateral oophorectomy

Note: Documentation can come from the site personnel's review of the participant's medical records, medical examination, or medical history interview.
- Postmenopausal female
  - A postmenopausal state is defined as 12 months of amenorrhea in a woman over age 45 years in the absence of other biological or physiological causes.

### 15.2.2 Contraception Guidance for Women of Childbearing Potential

One of the highly effective methods of contraception listed below is required during study duration and until the end of relevant systemic exposure, defined as 120 days after last treatment. Local laws and regulations may require use of alternative and/or additional contraception methods.

#### Highly Effective Contraceptive Methods That Are User Dependent

Failure rate of < 1% per year when used consistently and correctly.a

- Combined (estrogen- and progestogen-containing) hormonal contraception associated with inhibition of ovulation
  - oral
  - intravaginal
  - transdermal
- Progestogen-only hormonal contraception associated with inhibition of ovulation
  - oral
  - injectable

